A current limitation of monitoring in the ICU is the lack of methods for continuous, non-invasive capture of blood pressure (BP). In critically ill patients, clinicians rely on intra-arterial BP monitoring (IA-BP), whereby a catheter is inserted into the umbilical or other central or peripheral artery to provide continuous BP measurements. However, IA-BP procedures are invasive and lead to complications, thereby escalating risks of infection, bleeding, and thrombosis, increasing discomfort, and reducing contact. Thus IA-BP is only utilized in the most critically ill patients and is typically discontinued within 1 week. In the rest of the ICU population, only periodic cuff-based BP (CB-BP) measurements are obtained. CB-BP recordings are captured periodically, can be difficult to obtain, are disruptive, especially during sleep, and are highly unreliable. The lack of real-time and continuous monitoring of hemodynamic signals impairs the clinical team's ability to detect and promptly respond to acute risks of decompensation, as well as obscuring longer-term patterns which may be sensitive markers of developing instability.

The purpose of this study is to develop biocompatible electronic devices that will allow continuous, non-invasive hemodynamic measurements in the ICU (see sample figure 1 below). Members of this research team have developed innovative, wireless devices capable of being

[figure not shown]

Figure 1: Example of wearable sensor developed by the [name] group

comfortably and continuously worn while recording diverse physiologic measurements. These devices have already demonstrated the capability to accurately capture hemodynamic measurements in healthy adult subjects (unpublished data, see figure 2 below). We propose to 1)

optimize these devices for use in pediatric ICU patients, 2) demonstrate safety, reliability, and accuracy of these devices for continuous ICU hemodynamic signal measurements, including but not limited to BP, heart rate (HR), cerebral blood flow, temperature, and respiratory rate, and 3) demonstrate these devices are preferred by patients and parents to current measurement tools. Once validated, such sensors could fundamentally change the way patients are monitored in the ICU, eliminating risks associated with invasive monitoring, allowing continuous, real-time detection of clinically meaningful changes in ICU patients, advancing knowledge of hemodynamic signatures preceding clinically meaningful events, and ultimately offering opportunity to reduce morbidity and mortality in ICU patients.

[figure not shown]

Figure 2: Example of physiology measurements using wearable sensor. (A) ECG time waveforms for commercial cardiac monitoring device (red) and wearable sensor (blue). (B) Snapshot of average heart rate vs time using conventional ECG sensor (control) and wearable sensor in newborn. (C) Snapshot of oxygen saturation vs time using wearable sensor and standard oximetry sensor (control) in newborn. (D) PPG (blue) and ECG (red) waveforms captured simultaneously and synchronized in time in healthy adult subject. Pulse arrival time (PAT) interval denoted in the waveform. (E) Pulse arrival time measurements during rest, Valsalva maneuver and release in adult subject. (F) Correlation of systolic blood pressure (measured with cuff-based BP device) and PAT measured with wearable sensor in adult subject.

2. Study Hypothesis and Outcomes

2.1. Study Hypothesis

The main hypothesis of this study is that the wearable sensors will provide accurate, reliable, safe, and continuous capture of hemodynamic and physiologic signals in children, infants, and neonates.

2.2. Outcome Measures

2.2.1. *Primary Outcome*

Primary outcome measures: Recorded measurements of BP as compared to the ICU standard of care monitoring, including both arterial line measurements and cuff-based measurements of the arm.

2.2.2. *Secondary Outcomes*

Secondary outcome measures: Recorded measurements of other physiologic signals such as HR, pain, temperature, cerebral blood flow, aEEG-like waveforms, and respiratory rate as compared to ICU standard of care monitoring. Accelerometry will be captured using these devices, and in a subset of study participants, will be compared to video recordings to validate the accuracy of these devices for detecting body position and movement (as these are known to affect BP measurement). Devices may also evaluate subjects' respiratory equipment. Questionnaire data examining parent opinions on use of wearable sensors compared to standard of care devices.

3. Study Design

3.1. Target Population

Two distinct populations will be targeted for participation in this study. The first includes patients admitted to intensive care units (ICUs) including the pediatric intensive care unit (PICU), the neonatal intensive care unit (NICU), and the cardiac intensive care unit (CCU). This includes all ICUs at the Ann & Robert H. Lurie Children's Hospital of Chicago (Lurie Children's) and the NICU at Prentice Women's Hospital (Prentice). The first target population will contribute primarily to the collection and validation of physiologic signals including BP, HR, pain, temperature, cerebral blood flow, aEEG-like waveforms, and respiratory rate. The second target population includes any neonate, infant, or child whose parent or guardian consents to a one time visit to the Center for Autonomic Medicine in Pediatrics (CAMP) at Lurie Children's. The second population will be more physically active than the ICU population and contribute primarily to the capture and validation of these same physiologic signals in the context of increased motion, which is known to produce artifact in such recordings. The wearable sensors must be tested in a range of patients across age groups in order to validate the signals and data recorded by the devices. This requires the inclusion of patients of various ages, including neonates, infants, and children.

Up to 500 patients will be enrolled at Lurie Children's and Prentice.

3.2. Eligibility Criteria

3.2.1. *Inclusion Criteria*

Participants must be admitted to one of the three ICUs at Lurie Children's, admitted to the NICU at Prentice, or visiting CAMP with a parent or guardian. Anyone who satisfies one of these criteria and is under 18 years of age can participate.

3.2.2. *Exclusion Criteria*

Anyone with a skin abnormality that would potentially increase risk of device use will be excluded. Anyone 18 years or older will be excluded. In the ICU population, any patient or family determined by an attending physician or bedside care team to be too unstable (patient) or experiencing too much stress (family) will not be approached for recruitment.

3.3. Screening and consent

All ICU patients will be screened by the study team based on inclusion and exclusion criteria through review of electronic medical records. For screening at Prentice Women's Hospital, screening criteria will be automatically applied through the use of the electronic data warehouse, and information from infants meeting this screening criteria will be transferred to the study team through electronic data warehouse. A screening and enrollment log will be kept to track ICU patients/parents who have been approached and agreed or declined to participate in the study. The screening and enrollment log will be kept on the Northwestern University housed REDCap server. Only the study team will have access to this log. Non-ICU participants will be screened through question and answer with a parent or guardian.

3.4. Recruitment Methods

The population of ICU patients will be recruited by the study team as follows: once the study team has identified an eligible patient, the study team will obtain permission to approach the eligible patient from the nurse or attending, ensuring that the ICU care team has sufficient time to assess the condition of the patient and determine the family's approachability to discuss the study. If the family is felt to be approachable, the study staff will identify the best time to contact the family.

The population of non-ICU participants will be recruited by the study team using IRB-approved fliers distributed to affiliates of CAMP and posted in public locations in Chicago.

3.5. Informed Consent Process

All research staff will be trained on human subjects research education and good clinical practices, according to Lurie Children's IRB standards. A member of the study team will approach the prospective participant/family for consent using an IRB-approved consent form. Assent will be obtained from participants 12-17 years of age. If the prospective participant has a PCPC (Pediatric Cerebral Performance Category) score of ≥ 2 or has received sedative medications in the preceding 72 hours, assent will not be obtained. In the event that the participant is not capable of providing assent, a request for waiver of assent will be obtained from the IRB. If the cognitive capability of the participant changes during study participation and the participant is capable of providing assent, assent will be obtained within 48 hours.

In a private space, the study will be discussed in detail, including the rationale, the specifics of data collection, our legal and ethical obligations and procedures to ensure confidentiality, and the questionnaires. The study team will also discuss the risks of participation. The prospective participant/family will also be informed that involvement or refusal will not affect the care of their child, and will be completely optional and anonymous. The prospective participant/family will be informed that the video monitoring of body position and movement is an optional part of the study. Written material describing the nature of this study and a copy of the Informed Consent document will be provided to each family. The prospective participant/family will then be left with the consent form to review and will be given an opportunity for private discussion. They will have the opportunity to ask questions.

Once all questions are answered, the prospective participant/parents will be asked to discuss the study process in their own words before signing consent. To minimize the amount of time the study team spends in the participant's bed space, a participant's parent(s) may provide consent over the phone or a secure telecommunication platform such as Skype. The consent process as described above will not change. The family will be provided written materials describing the nature of the optional elements and given an opportunity for questions and private discussion.

Consent obtained over the phone or secure telecommunication platform will be obtained according to institutional policy. A member of the study team will explain in detail and review the informed consent document(s) with the parent(s). If the parent(s) agree to participation, they will sign a copy of the informed consent document(s) and the study team member obtaining consent will sign a copy at the same time. The parent(s) will be required to send their signed document(s) to the study team by mail, fax, or email, and the two signature pages will be combined. The parent(s) will be provided a copy of the fully executed, signed informed consent document(s) by mail, fax, or email prior to any study procedures.

For participants where a Waiver of Consent and/or HIPAA Authorization are used specifically for participants enrolled during COVID-19, the study team member approaching will review the entire consent form over the phone. In place of the signature, the study team member obtaining consent will ask the parents and/or adolescent about their interest to participate and get either a verbal consent (and/or assent) or refusal to participate.

If verbal consent and/or assent is obtained, the study team member obtaining permission will document that all the parts of the consent process were reviewed, and verbal consent was obtained on to the consent and/or assent with date and time, and sign attesting permission was obtained, and consent process was reviewed in the designated sections. A signed and completed copy of the consent and/or assent with the information stated above will be provided to the parents either via email or regular mail. The provided copy of the consent will not be returned in any form to the study team to ensure their safety.

3.6. Study Procedures

Device application: In both the ICU and non-ICU study populations, standard-of-care devices will be used in all subjects and this data will be compared to that collected using novel wearable sensors suggested in this study. After participants are consented, multiple wearable sensors (up to 5) will be placed on the participant for the duration of the study. Multiple devices are required to estimate BP. One or more devices will be placed on the chest or back, and one or more additional devices will be placed peripherally (e.g. leg, foot, arm, hand, head, or ear). One or more additional devices may be placed on the patient's respiratory support device if applicable. Placing multiple devices will allow determination of which location provides the best signals in specific populations. These devices will be placed using a medical grade skin adhesive similar to the ones used in the ICUs, which will minimize the

risk of skin irritation or allergic reaction. Alternatively, we are currently testing a “soft wrap-around device” (similar to that currently used for blood pressure monitoring in the premature babies) with a sensor. The soft wrap-around device is composed of hypoallergenic cotton. Overlying this cotton, and not touching the subject’s skin, may include Coban wraps, paper tape, or a Velcro adhesion mechanism. Given the very small size of premature infant in the NICU, we may incorporate this new technology as needed in the NICU. In the ICU population, devices will be left in place for up to 72 hours, but will either be checked by the study or clinical team to ensure skin integrity and signal quality at least once every 24 hours. In the non-ICU population, devices will be left in place for up to 3 hours during a study visit to CAMP.

We have recently upgraded a new firmware version activating the ability for the sensor to continuously measure bioimpedance for respiratory rate. This function does not require any modification to the physical device itself or the adhesive. However, the bioimpedance functionality does require delivery of low amplitude sinusoidal current through the electrodes of the chest unit. The frequency of the current is 4 kHz – a frequency range used typically for human bioimpedance measurements by FDA cleared systems. The maximum current delivered is 8 μ A. These parameters are below commonly used body fat percentage impedance analyzers that are widely commercially available. Furthermore, bioimpedance is standard measurements in existing NICUs / PICUs/CICUs leveraging the ECG electrodes that are then displayed on standard of care monitors. Commercially bioimpedance devices that are FDA approved inject currents that are 10x greater than our system (e.g. the CoVa Monitoring System 2 for continuous wearable sensing of thoracic impedance). Finally, the parameters in our sensor follow IEC 60601-1-2 guidelines for electromagnetic safety.

Video monitoring: In some participants, video monitoring of participant position and movement will be utilized during the study. This is an optional, additional part of the study in which families can choose to participate or not participate. If a family chooses to participate, a video camera will be utilized to capture participant movement and position for the duration of the study in the ICU or at CAMP.

Cuff-based blood pressure: While the wearable sensors are attached to participants in both the ICU and non-ICU populations, the participants will also be monitored with the normal standard of care monitoring montage. In addition, during one 3- or 4-hour period while the wearable sensors are attached to the patient, a member of the study team may take the participant’s BP using the ICU standard cuff-based method every 15 minutes. Cuff-based measures typically happen every 15-60 minutes for standard clinical care, depending on the stability of the patient and physician discretion. In the ICU population, if a standard clinical cuff-based BP measure is taken during the 15-minute time epoch, the clinical measurements will be used rather than obtaining a separate research measurement. Outside of this 3- or 4-hour window and for the remainder of the study duration in the ICU cohort, cuff-based BP measures will be made only as frequently as needed for standard clinical care.

Skin temperature: While the wearable sensors are attached to the participant, skin temperatures will be taken using a standard infrared thermometer. These measurements will be made at the same interval as the above cuff-based BP, over the same 4-hour period by a member of the study team. Outside of this 4-hour window, no skin temperature measures will be made for research purposes.

Device data: Wearable sensors can stream data continuously using near field communication (NFC) or Bluetooth technology. An encrypted laptop, iPad, or similar device will be left in the patient room and used to capture the continuous data stream from the wearable sensor. Additionally, wearable sensors can include onboard memory, and physiologic streams may be recorded to this onboard memory until transfer to an encrypted laptop for analysis.

Standard of care data: In all participants where data from standard of care monitoring is captured and stored using the BedMasterEx system (all PICU and CCU beds, some NICU beds), and the Sickbay™ platform (CCU beds), this data will be used for comparison to data captured using EWP. In any participants where data are not captured and stored using the BedMasterEx system or Sickbay™ platform, video recordings will be made of the Phillips monitors using an encrypted mobile device. Within 48 hours, videos will be downloaded and transferred to a HIPAA secure server. In NICU patients without BedMasterEx data, the Somnostar system may be used to capture data for up to 4 hours of the study. All study data will be stored on an encrypted laptop and/or secure network for analysis. We will continue to follow patients for 5 years by collecting standard of care data entered into their electronic medical record.

Skin Integrity: Before and after wearable sensors are placed on the participant, the participant's skin integrity will be monitored using the ICU standard protocol, either the Braden Q scale (≥ 6 months of age) and/or Neonatal Skin Risk Assessment Scale (NSRAS; < 6 months of age). Additionally, a validated skin integrity scale will be used to score participants' skin condition at sensor placement site before sensor placement and immediately after sensor removal. At both of these time points, photographs may be taken of the participants' skin at the site of sensor placement to document any skin changes that occur during the period of wearable sensor wear. No faces will be photographed. One or more additional skin scores and photographs may be performed/taken between 30 minutes and 48 hours after sensor removal, as deemed necessary by the study and/or clinical team. The study team will consult the ICU bedside care team or CAMP clinical team within 1 hour for any concerning changes in skin integrity.

Questionnaires: After the study period ends, the parents may be approached to complete the questionnaires. These questionnaires will take less than 10 minutes to complete and are meant to assess opinions on use of these devices in the ICUs. These questionnaires will be completed using REDCap. If preferred, the family will complete a printed version of the REDCap questionnaire and this data will then be entered by study staff into the REDCap server. All questionnaire data will be stored on the secure REDCap server housed by Northwestern University.

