3.7. Study Timeline

Study recruitment, data collection, and ongoing analysis: 1-30 months
Final analysis and report preparation: 6 months

4. Study Safety

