5.2. Statistical Plan

Measurements made through clinical standard of care will be compared to the measurements recorded by the wearable sensors. Distribution checks for normality and data accuracy will be completed for each individual and for the entire study prior to all analyses. For continuous measures of physiology, 30 second epochs will be defined for each method for comparison. For non-continuous CB-BP measures, each measure will be matched and compared to the 30-second epoch during which the measure was captured. We will further check for time lags in the relationships between methods by applying peak-picking methods to lagged regression plots for all pairs of measures.

Agreement and correlation of wearable sensor measures to standard of care measures will be assessed in two ways. First, Bland-Altman plots will be created to assess agreement between each measurement system via bias and precision, which reflect the mean or average difference between two methods and the variation in these differences, respectively. Our second method consists of individual correlations between methods assessed for each person. This correlational method will supplement additional methods, and can be directly transformed to variance shared between wearable sensor and standard of care measures, a common metric of reliability of any measure.

Formal tests of bias, precision, and correlations: While the above methods will yield useful statistics, they need to be extended to deal with the structured nature of our data. Specifically, our data are clustered, meaning that we have multiple observations within each person and multiple people in our sample, which violates standard independence assumptions inherent to many models. We propose to estimate bias and correlation/reliability using multi-level models, which yield the same statistics discussed above but account for the fact that observations taken from the same patient are more related than comparisons involving different patients.

Statistical power: The large amount of within-person data provides incredibly high statistical power for all planned and many secondary data analyses, allowing this data set to answer all proposed questions. Previous work on power in multilevel models found greater than 99% power to detect associations with the planned observations suggested here within comparable nested designs.

6. References

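### Does choosing sensor sites and checking lags in the same children used to show accuracy bias the reported agreement?

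*Protocol*

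**What the plan says.** The aims in the Protocol's introductory section put development and validation in one study: to "optimize these devices for use in pediatric ICU patients" and to "demonstrate safety, reliability, and accuracy of these devices for continuous ICU hemodynamic signal measurements". Section 3.1 gives a single pool of up to 500 patients, with no division into development and validation groups.

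Section 3.6 allows up to five sensors per child and states: "Placing multiple devices will allow determination of which location provides the best signals in specific populations". It also describes a wrap-around form still under test and adds "we may incorporate this new technology as needed in the NICU". Section 3.7 lists "Study recruitment, data collection, and ongoing analysis: 1-30 months", followed by a separate six-month period for final analysis and reporting.

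For cuff readings, Section 5.2 says "each measure will be matched and compared to the 30-second epoch during which the measure was captured". It then says the team will "check for time lags in the relationships between methods by applying peak-picking methods to lagged regression plots for all pairs of measures". Research cuff readings are described in Section 3.6 as "BP using the ICU standard cuff-based method every 15 minutes", over one period of 3 or 4 hours.

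**The concern.** Accuracy measured in the data used to choose a configuration is optimistic. The site with the smallest apparent error is partly the best site and partly the luckiest. A correlation read off at the peak of a lag scan is at least as large as the one at a fixed lag. The protocol has several such choices open (site by population, device form in the NICU, lag for every pair of measures), analyses during recruitment, names no lock and sets no children aside.

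Blood pressure agreement is the primary outcome, and the introductory section looks ahead to sensors that remove the risks of invasive monitoring. Overstated agreement would therefore matter. Multilevel models deal with clustering but not with selection, and the power statement in Section 5.2 concerns detecting associations, so neither answers the point.

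**Working it through.** The protocol gives no figure for agreement error, so there is none to reproduce. Sizes below rest on stated assumptions.

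**Inputs from the Protocol**
- Up to 5 sensors per child, at least one on the chest or back and one peripheral (3.6), so at most 5 - 1 = 4 competing peripheral sites.
- Cuff readings every 15 minutes for 3 or 4 hours (3.6): 12 to 16 per child.
- 30-second epochs (5.2): 3 h x 120 = 360, or 72 h x 120 = 8,640.
- Up to 500 children (3.1) over five settings (3.2.1): 100 each if split evenly.

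**Assumptions**
- Between-child SD of error 5 mmHg and within-child SD 6.245 mmHg, so total error is sqrt(25 + 39) = 8 mmHg.
- Truly equal sites, which is the worst case for selection.
- Correlation of child-level error between sites 0 or 0.5.
- 12 to 8,640 pairs per child.

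**Site selection (simulation).** Shortfall in apparent root-mean-square error when the lowest of four sites is reported:

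| Children | Shortfall | Shift in a limit, 1.96 x 8 x shortfall |
|---|---|---|
| 20 | 5.8-8.0% | 0.9-1.3 mmHg |
| 100 | 2.7-3.5% | 0.4-0.5 mmHg |
| 500 | 1.2-1.6% | 0.2-0.25 mmHg |

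With two sites and 500 children it is 0.5-0.9%. With a single pre-fixed site it is within about 1%.

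Counting one difference per child and taking the smallest SD of two to four sites gives more: 9-18% at 20 children, 4-8% at 100 and 2-3% at 500. That ignores the 12 to 16 readings per child and the repeated-measures model in Section 5.2.

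**Against sampling error, on a matching basis**

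*One difference per child.* Half-width of the 95% interval for a limit = 1.96 x 8 x sqrt(1/n + 1.96²/(2(n-1))). For n = 100: 15.68 x sqrt(0.0100 + 0.0194) = 2.7 mmHg. The 4-8% shortfall is 15.68 x 0.04 to 0.08 = 0.6-1.3 mmHg. For n = 20 the half-width is 6.1 mmHg against 1.4-2.8 mmHg.

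*Twelve pairs per child.* The variance of a child mean is 25 + 39/12 = 28.25.
- At n = 100, SE of the mean difference = sqrt(28.25/100) = 0.53.
- SE of the total SD = sqrt[2 x 28.25²/99 + 2 x (39 x 11/12)²/(100 x 11)] / (2 x 8) = 0.27.
- Half-width = 1.96 x sqrt(0.53² + 1.96² x 0.27²) = 1.5 mmHg.
- The 12-pair shortfall at n = 100 is 3.3-3.5%, or 0.5 mmHg.
- The same steps give 3.3 mmHg against 1.2-1.3 at n = 20, and 0.65 against about 0.25 at n = 500.

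On either basis the optimism is less than half the half-width.

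**Lag picking (simulation, autocorrelated signals, 11 lags of 30 seconds, autocorrelation 0.5 or 0.9)**

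| Data | True r | Mean r at zero lag | Mean r at picked lag |
|---|---|---|---|
| 12 cuff pairs | 0 | 0.00-0.01 | 0.25-0.42 |
| 12 cuff pairs | 0.5 | 0.47-0.48 | 0.59-0.60 |
| 12 cuff pairs | 0.8 | 0.79 | 0.80-0.82 |
| 360 epochs | 0.5 | 0.50 | 0.50 |
| 8,640 epochs | 0.5 | 0.50 | 0.50 |

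So lag picking matters only for sparse cuff pairs realigned at the picked lag. Section 5.2 gives cuff readings the opposite rule, same-epoch pairing, under which mean r is within 0.03 of the truth.

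**Can it be settled later?** A child's sensors record at the same time and their data are kept (3.6, 4.1). Reporting every site, keeping zero-lag pairing, cross-validating or splitting by enrolment date are all open until the final analysis (3.7).

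**The case for a change.** The strongest case for a change is that some of this is conduct, not analysis. Which device form a child wears is decided at the bedside, and a later analysis plan cannot create children who were untouched by development, nor recover a version nobody recorded. Section 3.6 looks for the best site in specific populations, so small groups are realistic, and more epochs per child barely help: with four independent sites and 20 children the shortfall is 8.0% with 12 pairs and still 6.7% with 8,640. A lock would be cheap: basing the claim on 400 of 500 children widens the half-width from 1.2 to 1.3 mmHg (one difference per child).

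Part of this stands. Device form is a matter of conduct, and recording form and firmware version with each recording is good practice. The protocol does not say they will go unrecorded, though. It presents the wrap as an alternative attachment for very small infants, not as one chosen for better agreement. It describes no tuning of a blood pressure algorithm on these children's reference readings, and the reported firmware upgrade concerns respiratory rate, a secondary outcome. Signal quality may also be judged without the reference, and if so unrelated to error, in which case the site bias is nil. The cost of a lock is quoted for the pooled 500, whereas the harm is claimed in small groups, where losing participants costs most.

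**Conclusion.** No change is needed. The protocol does combine optimisation, site comparison and accuracy in one cohort and leaves the time of fixing site and device form unstated. That is missing detail which analysts can supply, not a rule that produces biased results. The stated cuff pairing is already the safe one, and the quantified site and lag effects can be removed at analysis without discarding anyone. Limiting the accuracy claim to children enrolled after a lock is a design preference.

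If only the best-looking of four sites were reported, error would be understated by 1.2-1.6% in the pooled 500, about 3% at 100 and 6-8% at 20. This assumes equal sites, a true error of 8 mmHg and the variance split above; a clearly superior site would give less. The lag effect is close to nil for long recordings of related signals, and for cuff data arises only if the stated pairing is overridden.

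### ICU group: the single research window for cuff BP and skin temperature is not tied to time since sensor placement, and agreement is summarised without any breakdown by wear time

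*Protocol*

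**What the plan says.** Wear time (Protocol Section 3.6, device application): "In the ICU population, devices will be left in place for up to 72 hours". Someone from the study or clinical team looks at the sensors "to ensure skin integrity and signal quality at least once every 24 hours". For the other population, "In the non-ICU population, devices will be left in place for up to 3 hours during a study visit to CAMP".

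Research cuff readings (Section 3.6, cuff-based blood pressure): "during one 3- or 4-hour period while the wearable sensors are attached to the patient", a team member "may take the participant’s BP using the ICU standard cuff-based method every 15 minutes". The text does not say when, relative to placement, this period should begin. Infrared skin temperatures follow the same interval and period, and the section rules out research skin temperatures outside it.

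Clinical cuff readings: "Cuff-based measures typically happen every 15-60 minutes for standard clinical care", with the rate depending on how stable the child is and on the physician's judgement. For the rest of ICU wear, "cuff-based BP measures will be made only as frequently as needed for standard clinical care".

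Analysis (Section 5.2): continuous signals are compared in 30-second epochs and every cuff reading is matched to its epoch. Bias is "the mean or average difference between two methods" and precision is the variation of the differences. Multi-level models are proposed because readings are clustered within children. Time lags between methods are considered; hours since placement are not mentioned.

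**The concern.** The hypothesis in Section 2.1 claims capture that is accurate and also continuous. For a sensor worn up to three days, that includes accuracy on day 3. The protocol itself arranges for signal quality to be looked at again during wear, but that check does not compare the sensor with a reference.

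The research cuff series is the only cuff reference at regular times that do not depend on the child's condition. It is taken once per child, and nothing prevents every window from falling in the first hours after placement, when sensors are fresh. The evenly timed evidence would then describe new sensors only. The infrared skin temperatures, which bear on a secondary outcome, would stop there altogether.

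A single pooled bias adds to the problem: a change in accuracy over wear is partly or wholly averaged away in the mean, and adds little to the limits of agreement when ordinary scatter is large.

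**Working it through.** The plan states no figure for agreement over wear, so there is none to reproduce. The schedule inputs come from Sections 3.6 and 5.2. **All drift sizes and SDs below are assumptions; the documents give none.**

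**1. Share of wear covered by the research window**
- 3/72 = 4.2%; 4/72 = 5.6%.
- Readings at one per 15 minutes: 3 × 4 = 12 or 4 × 4 = 16 (13 or 17 if both ends are counted).

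**2. What else samples late BP**
- With a 4-hour window at the start, 72 - 4 = 68 hours remain. At the protocol's typical clinical rate of one reading per 60 to 15 minutes, this gives 68 to 272 clinical cuffs.
- After hour 24: 48 to 192. After hour 48: 24 to 96.
- Research share of all cuff readings: lowest 12/(12 + 276) = 4.2% (3-hour window, clinical cuffs every 15 minutes); highest 16/(16 + 68) = 19.0% (4-hour window, hourly clinical cuffs).
- Children with an arterial line add 30-second epochs while line and sensors are both in place; a full 72 hours would be 72 × 120 = 8,640 epochs.

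**3. Drift through zero, from -d to +d over 72 hours, SD of differences 6 mmHg without drift**
- Pooled bias = 0; total SD = √(36 + d²/3); limits = ±1.96 × SD.

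| d (mmHg) | Total SD | Limits | Bias at hour 72 |
|---|---|---|---|
| 0 | 6.00 | ±11.8 | 0 |
| 2 | 6.11 | ±12.0 | +2 |
| 4 | 6.43 | ±12.6 | +4 |
| 6 | 6.93 | ±13.6 | +6 |

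**4. One-directional drift, from 0 to D over 72 hours**
- Pooled bias = D/2; bias by day = D/6, D/2, 5D/6. A 4-hour window is centred at hour 2 if first (2D/72) and at hour 70 if last (70D/72). With an assumed SD of 8 mmHg, total SD = √(64 + D²/12).

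| D (mmHg) | Pooled bias | Day 1, 2, 3 | Window first / last | Total SD |
|---|---|---|---|---|
| 2 | 1.0 | 0.33, 1.00, 1.67 | 0.06 / 1.94 | 8.02 |
| 5 | 2.5 | 0.83, 2.50, 4.17 | 0.14 / 4.86 | 8.13 |
| 10 | 5.0 | 1.67, 5.00, 8.33 | 0.28 / 9.72 | 8.50 |

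**5. Does an early window dominate the pooled cuff bias?** Take D = 5.
- Hourly clinical cuffs: 16 research readings at mean hour 1.875 and 68 clinical readings at mean hour 37.5. Mean hour = (16 × 1.875 + 68 × 37.5)/84 = 30.7, so pooled bias = 5 × 30.7/72 = 2.13.
- Clinical cuffs every 15 minutes: pooled bias 2.49.
- Evenly spread readings would give about 2.5, so at these rates an early window shifts the pooled figure little.

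**6. Can drift be estimated from data already collected?** Per child, with SD 8 mmHg and readings treated as independent, the standard error of the change over 72 hours is 8/√Σ(x - x̄)², where x = hours/72.
- 4-hour window alone: Σ = 21.25/5,184 = 0.0041, so the standard error is 125 mmHg.
- With hourly clinical cuffs added: 2.8 mmHg. With 15-minute clinical cuffs: 1.6 mmHg.

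Within a child, the research window carries almost no information on drift. Across the wear it becomes informative only if its start varies between children. The clinical readings make a breakdown by day feasible.

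**The case against.** A reader might infer that BP accuracy in late wear is never sampled. The protocol does not support that. Clinical cuffs continue throughout ICU wear, Section 5.2 matches each of them to its epoch, and the arterial line is a primary reference too. At the typical clinical rate the research series is a minority of the cuff readings, and an early window would not drive the pooled bias. This part of the objection stands in full.

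A reader might also infer that the analysis is committed to a bias that is constant over wear. It is not. Section 5.2 lists no model covariates, so it does not exclude a wear-time term, and such a term is commonly left to a statistical analysis plan. Its absence alone would not be a finding.

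Nor do the documents report or predict drift. The 24-hour check is a safeguard, and the symmetric drift in step 3 is the shape that makes the pooled bias exactly zero; a one-directional drift leaves half its size visible.

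What the objection does not remove is the timing of the window, which is a study procedure: no later analysis can create late research readings that were not taken. The late BP data are also selected. Clinical cuff frequency follows the child's condition, and by the protocol's introduction intra-arterial monitoring is confined to the sickest patients. For research skin temperature there is no substitute infrared reading outside the window.

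**Conclusion.** The point holds for the ICU group only. Non-ICU wear is at most 3 hours, so there is no late wear to miss.

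The research window covers at most 5.6% of a 72-hour wear and is not anchored to placement. If windows cluster early, the evenly timed cuff series is silent on days 2 and 3, and the infrared skin temperatures have no later reading. Late BP would then be sampled, but only by readings whose timing or availability depends on the child's clinical state.

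The stated summary, a mean difference, can mask change over wear. Under the assumed drift from -4 to +4 mmHg with SD 6 mmHg, pooled bias is 0 and the limits move from ±11.8 to ±12.6 mmHg while bias at hour 72 is +4 mmHg. A one-directional drift of D appears as D/2. These sizes are illustrations, and the counts of late clinical cuffs assume a full 72-hour wear at the typical clinical rate.

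This is a worthwhile, inexpensive improvement to a hypothesis that rests on continuous accuracy. It does not show that the sensors drift or that the planned comparison is invalid.

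**What to change.** 1. In Section 3.6, spread the start of the existing research window over the ICU wear period between children, for example by assigning each child an early, middle or late start in advance. The number of readings per child does not change.
2. Record the time of sensor placement and removal. Placement time is not named in the list of data to be collected in Section 4.1.
3. Using all matched research cuff, clinical cuff and arterial-line data, report bias and limits of agreement for 0-24, 24-48 and 48-72 hours, with hours since placement in the multi-level model. Show the results by reference method, because late clinical cuffs and arterial lines come from selected children.
4. Repeat the table in children still wearing sensors in the last interval, so that a change over wear is not confused with a change in who remains.

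Cost: staff scheduling, one or two extra time stamps, one model term and one table. Some windows assigned to day 2 or 3 will be lost when sensors come off before 72 hours; the number lost should be reported.
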